The PI will work closely with the research coordinator and the co-investigators to screen and identify appropriate subjects listed on the daily operating room schedule at the Liberty Campus of CCHMC according to the inclusion and exclusion criteria defined in the study protocol. Once a potential subject is identified, either the PI or the research coordinator will discuss the purpose and procedures of the study with the patient and his or her guardian(s). Hospital-approved interpreters will be utilized for non-English speaking patients and/or guardian(s). Participants and their guardians will be informed of the voluntary nature of participation and the ability to drop out of the study at any time without negative consequences. If the guardian(s) express interest in participating in the study, they will be asked to read the written informed consent. When appropriate, assent or consent to participate will be obtained from the patient. Written assent will be obtained from the patient if the patient is ≥ 11 years of age and is able to provide written assent, which represents standard policy with regards to age of assent at CCHMC.

To allow for the broadest application of clinical outcomes, enrolled subjects will vary in their physical characteristics to the greatest extent possible given the inclusion and exclusion criteria.

1. Preparation:

Following identification of a potential subject, the patient and/or his/her parent(s)/guardian(s) may be called prior to scheduled surgery to initiate the informed consent process and to determine family interest in participation. If the patient and/or guardian(s) express interest during the phone call and the patient qualifies for the study, the family will be approached in Same Day Surgery by one of the study team members to

complete the informed consent process. Once all questions have been answered and the informed consent signed, the patient will be enrolled in the study at which time the subject will be assigned a study identification number. Written assent will be obtained if the child is ≥ 11 years of age and is able to provide written assent.

2. Vulnerable Populations:

Children from 10 years to 18 years of age (inclusive) will be recruited for this study after obtaining written informed consent from their parents and assent when appropriate (age >11 years).

D. Sample Size Determination:

Power analysis was performed to estimate an adequate sample size to support statistical conclusion validity and so that correct inferences can be made about the relationships between study variables. The standardized effect size was calculated to equal 0.5. Assuming an alpha of 0.05, power of 0.80 and a standardized effect size of 0.5, 64 patients will be required for each treatment group based on anticipated difference in patient reported pain scores due to sciatic PNB technique. Projected sample sizes were increased approximately ten percent from 64 per group to total of 70 subjects per group in an effort to account for patient attrition and lost data, therefore, a total of 140 patients will be enrolled in the study. Additionally, if the loss in patients is unequal between groups, yielding a significant disparity between study group composition, additional subjects may be added to account for this unequal loss.

Despite the presence of multiple confounding variables, the calculated sample size is sufficient to determine if a significant difference in outcomes measures exists secondary to sciatic PNB technique. Additionally, the sample size does not need to be altered based on the equation: $N > 50 + 8k$, where N is the number of cases and k is the number of predictors (Warner, 2013). In this study there is only one predictor, sciatic PNB technique, which is anticipated to impact outcomes following ACL reconstruction.

E. Randomization:

A computer generated randomization scheme will be used to assign 70 patients to each treatment group. The randomization will be done using the maximum allowable percent deviation method. This algorithm conducts a search to find a randomization list for which all percent deviations are less than or equal to the maximum allowable percent deviation of 10%. The randomization scheme will be sent to the PI who will then prepare and maintain a log of subject assignments. The PI will notify the participating surgeon and anesthesia team of the treatment (single-injection or continuous sciatic PNB) that is to be given to the next consented patient. The research coordinator will remain blinded to the assigned treatment plan until data collection has been completed.

F. Components of Cincinnati Children's Hospital Medical Center to be Utilized for this Study:

Subjects undergoing unilateral ACL reconstruction with a hamstring autograft on an outpatient basis at the Liberty Campus of CCHMC will be recruited from the OR schedule.

G: Data Collection:

Participants will be in the research study for approximately 4 days; the day of surgery and for follow-up phone calls once a day for the first three days after surgery. A minimum of three phone calls may be made after the patient is discharged. Once enrolled in the study, a unique study identification number will be assigned to each study participant. Assigning a unique patient identifier to each study participant allows any data gathered pertaining to them to be attached to this number rather than any patient identifiers, further ensuring that a breach in confidentiality does not occur (Polit & Beck, 2012). After obtaining written consent from the guardian(s), the medical record of the patient will be reviewed for further inclusion and exclusion criteria.

All data gathered will be used specifically for research purposes. Data collected preoperatively will include age, gender, BMI, ASA physical status, previous surgical history, self-reported tolerance of pain, self-reported level of activity since time of ACL injury, and the name of the orthopedic surgeon scheduled to perform ACL reconstruction. In addition, several questions regarding the patient's anxiety level will be asked to determine whether or not the patient has a history of anxiety that may impact pain and/or satisfaction scores postoperatively (see Appendix A). This data will be collected from the patient's medical record during the preoperative phase and directly from the patient and/or guardian(s) when appropriate. Data on study group assignment, analgesic requirement, the length of surgery, length of pneumatic tourniquet inflation time, pneumatic tourniquet inflation pressure, and systolic blood pressure at time of pneumatic tourniquet inflation will be gathered during the intraoperative phase.

In an effort to discern the impact of sciatic PNB technique on the outcome measures, data on self-reported pain scores, doses of oral pain medications, unplanned admission to the hospital due to poor pain control, and patient satisfaction will be gathered while the patient remains in the post anesthesia care unit (PACU). Data collection will then continue for 72 hours postoperatively following discharge from the PACU. Patients will document data measures on supplied data collection instruments (see Appendix B).

The patient or their guardian will record pain scores once every 6 hours for 72 hours postoperatively. In addition, the patient or their guardian will note the

date and time their leg was no longer numb behind their knee. The orthopedic surgeon performing the ACL reconstruction or a member of his orthopedic team will prescribe all postoperative oral pain medication. The oral pain medication typically prescribed is either Percocet or Vicodin. Vicodin, a schedule 3 controlled substance, is approximately half as potent as Percocet, which is a schedule 2 controlled substance. The patient will record the time and dose of all oral pain medication taken during the 72 hours postoperative period. The patient or their guardian will also record data regarding pain associated with active knee flexion once every 12 hours for 72 hours postoperatively. In addition, the patient or their guardian will record satisfaction with pain control once every 12 hours for 72 hours postoperatively.

The research coordinator may collect all data recorded by the patient and/or their guardian via telephone interview. Data will be collected using the same data collection tool given to the study participants to avoid instrumentation and maintain interrater reliability. Untoward events, such as unplanned hospital admission, CPI catheter dislodgement, or local anesthetic toxicity, will also be noted should they occur. This information will be collected from the patient or guardian once every 24 hours by the research coordinator during the 72-hour postoperative period; the postoperative period begins at the time of discharge from the PACU.

1. Survey(s) and Questionnaire(s):

Patients and their guardian will be given data collection instruments to complete postoperatively at the time of enrollment to facilitate recall when conveying information to the study staff during telephone conversations. The data collection instruments will be available in different languages and utilized for non-English speaking patients and/or guardians. The patient and their guardian(s) will receive training regarding the data collection tool both during the time of enrollment and again prior to discharge from the hospital. At the time of enrollment, essential phone numbers, including home phone and cell phone numbers, will be collected. Should the patient and/or guardian lose the data collection sheet, additional copies can be emailed to them upon request. Hospital-approved interpreters will be utilized for non-English speaking patients and/or guardian(s).

The goal of the data collection tool is to promote accurate data recording, limit the likelihood of missing information, and to promote efficient and accurate data entry into REDCap™. Prior to the start of study enrollment, the data collection tool will be piloted in an effort to reduce error in the measurement process. Five volunteers undergoing ACL reconstruction with a hamstring autograft at the

Liberty Campus of CCHMC will be sought out to trial the data collection tool. Refinement of the data collection tool will center on reliability and validity of the tool. Focusing on stability, internal consistency, and interrater reliability during the pilot of the tool will allow for estimates of the tool's reliability. Stability, or test-retest reliability, is determined by administering the tool two different times to the same individuals and determining the correlation between the two sets of scores (Kimberlin & Winterstein, 2008). Cronbach's alpha, which is a function of the average intercorrelations of items and the number of items in the scale, is the most widely used method for estimating internal consistency (Kimberlin & Winterstein, 2008). Interrater reliability requires completely independent ratings of the same event by more than one individual (Kimberlin & Winterstein, 2008). Tests of the tool's validity will focus on construct validity, content validity, and criterion-related validity. Evaluation of construct validity requires an examination of the relationship between the outcome measures being evaluated and variables related to the construct being measured by the instrument (Kimberlin & Winterstein, 2008). As there is no statistical test to determine whether a measure adequately represents a construct, content validity typically relies upon the judgment of experts in the field (Kimberlin & Winterstein, 2008). Assessment of criterion-related validity will focus on the tool's ability to accurately predict how well the scores of a given measure correlate with the scores of the other measures of the same construct. Revisions will be made to the data collection tool as necessary prior to the start of the study.

H. Period of Time Estimated to Complete the Study:

Each enrollment will take variable time to complete depending on the length of the surgical procedure and amount of time required in the recovery room. Following enrollment, data is collected for 72 hours postoperatively. The entire study will take approximately 2 years to enroll and complete.

VI. DATA STORAGE AND STATISTICAL ANALYSIS

A. Data Storage:

Data confidentiality will be maintained by data being stored in a password protected computer and hard copies of subject information stored in a locked office. All data is collected from the study participant will be entered into REDCap™ (Park City, Utah) by the research coordinator. REDCap™ is a secure web application for building and managing databases securely that was specifically designed to support clinical and translational research

(Harris, Taylor, Thielke, Payne, Gonzalez, & Conde, 2009). Confidentiality of the data will be maintained through the use of a password-protected computer and any hard copies of subject information stored in a locked office accessible only to members of the Department of Anesthesia.

The study records will be made available for review only to the Institutional Review Board and the Food and Drug Administration (FDA) per CCHMC policy. The FDA is a branch of the federal government that establishes regulations and guidelines for clinical research to protect participants from unreasonable risks. Furthermore, the FDA ensures consumers have reliable information and that medical treatments are not only safe, but effective as well. The subjects' names or any other identifiers will not be used in published information relating to this study and will be treated as confidential per the Health Insurance Portability and Accountability ACT (HIPAA) of 1996. Per the HIPAA Privacy Rule, prior to dissemination of results, all health information will be deemed individually unidentifiable by employing the approved Safe Harbor method of de-identification that entails the removal of 18 types of identifiers.

B. Primary Endpoint Analysis:

The hypothesis that the extended duration of analgesia offered by continuous sciatic PNB decreases pain scores during the initial 72 hours following hamstring autograft harvest when compared to single-injection sciatic PNB will be tested with two separate tests. Both Pearson's correlation and the Wilcoxon Mann Whitney test will be utilized to test his hypothesis, as controversy surrounds the analysis of Likert scale data. It has been argued that only nonparametric statistics should be used on Likert scale data, as the intervals between the scale values may not be equal (Jamison, 2004). Taking this into consideration, the pain scores recorded for each patient will be totaled and an average pain score will be calculated for each study participant. This will allow the data to be measured on a continuous scale, thereby meeting the criteria of Pearson's correlation. Pearson's correlation is a parametric test that measures the degree and direction of linear relationship between two variables (Gravetter & Wallnau, 2000). The Wilcoxon Mann Whitney test will also be used to analyze pain scores recorded at each 12-hour period to determine if there is a difference in outcomes related to the duration of analgesia provided by sciatic PNB technique. This test is appropriate when there is one IV with two independent groups and the DV is ordinal in nature. The Wilcoxon Mann Whitney test is a nonparametric test of the null hypothesis that two populations are the same against an alternative hypothesis. This test uses the relative position of the data in a rank ordering, rather than the actual values. Using both parametric and nonparametric tests will increase confidence when drawing conclusions should both tests lead to the same results.

The hypothesis that the extended duration of analgesia offered by continuous sciatic PNB decreases oral pain medication use during the initial 72 hours following hamstring autograft harvest when compared to single-injection sciatic PNB will be tested with the Independent Samples *t*-Test. The Independent Samples *t*-Test is appropriate when there is one IV with two independent groups and the DV is continuous in nature (Field, 2009). The Independent Samples *t*-Test is used to compare differences between separate groups when there are two experimental groups (single-injection sciatic PNB and continuous sciatic PNB) and different study participants have been used in each group (Field, 2009).

The hypothesis that the extended duration of analgesia offered by continuous sciatic PNB decreases the incidence of unplanned admission due to poor pain control during the initial 72 hours following hamstring autograft harvest when compared to single-injection sciatic PNB will be tested with the Chi-square test. The Chi-square test is used to determine if there is a relationship between two categorical variables (Field, 2009). As the data for this DV are categorical, the focus during analysis is placed on frequencies rather than means. The Chi-square test can be used to determine if there is a significant difference between the expected frequencies and observed frequencies in one or more categories (Field, 2009).

The hypothesis that the extended duration of analgesia offered by continuous sciatic PNB does not delay active knee flexion during the initial 72 hours following hamstring autograft harvest when compared to single-injection sciatic PNB will be tested using the Wilcoxon Mann Whitney test. The hypothesis that the extended duration of analgesia offered by continuous sciatic PNB improves patient satisfaction during the initial 72 hours following hamstring autograft harvest when compared to single-injection sciatic PNB will also be tested using the Wilcoxon Mann Whitney test. The Wilcoxon Mann Whitney test is appropriate to test both these hypotheses, as this test is designed to evaluate the difference between two treatments (single-injection sciatic PNB and continuous sciatic PNB) using data from an independent measures study (Gravetter & Wallnau, 2000). During analyses, testing may be altered based on the recommendations of the statistician to better analyze the collected data. Intention-to-treat analysis will not be employed, as this may skew results and it is often difficult to obtain outcome data for study participants who have dropped out of the study (Polit & Beck, 2012).

Prior to any analyses, the distribution of the demographic variables will be compared between the two treatment groups. All statistical tests will be two-sided with a significance level of $\alpha=0.05$ and will be conducted using SAS[®] software, (Version 9.2, Cary, NC). Following the enrollment of the initial 30 subjects (with 15 in each study group), an interim analysis utilizing the statistical tests later described will be performed to determine if statistically

significant differences exist between the outcome measures of each sciatic PNB technique. Performing an interim analysis limits the number of patients exposed to study procedures. If statistically significant differences exist such that one of the two sciatic PNB techniques clearly produces superior patient outcomes, the study will be stopped. However, should the outcomes measures of each sciatic PNB technique be found to be equivalent and without statistically significant differences enrollment will continue.

VII. DATA SAFETY AND MONITORING

Adverse events will be collected until data collection is complete. Adverse events will be recorded on the case report forms. Details will include an explanation of the event, seriousness, anticipation, treatment, resolution and relatedness to the study treatment. All study-related adverse events will be followed through to completion

A. Adverse Event Definitions:

The definitions for adverse event, adverse device effect, serious adverse event, serious adverse device effect, and unanticipated adverse device effect are provided below (ANSI/AAMI/ISO 14155-2:2003, 21 CFR 812.3(s)).

Adverse Event: an adverse event is any untoward medical occurrence in a subject, which need not be related to the treatment under investigation.

Adverse Peripheral Nerve Blockade Blockade Effect: an adverse peripheral nerve blockade effect is any untoward or unintended response to regional blockade, which may result from insufficiencies in the deployment of the ultrasound machine, or from provider error.

Serious Adverse Event: a serious adverse event is an adverse event that results in death, inpatient hospitalization, severe or permanent disability, a life threatening illness or injury, fetal distress, fetal death, a congenital abnormality, a birth defect, or medical or surgical intervention to prevent permanent impairment to body or structure.

Serious Adverse Peripheral Nerve Blockade Effect: a serious adverse peripheral nerve blockade effect is an adverse regional blockade effect that results in death, inpatient hospitalization, and severe or permanent disability or is life threatening.

Unanticipated Peripheral Nerve Blockade Effect: any serious adverse effect on health or safety or any life threatening problem or death caused by, or associated with, peripheral nerve blockade if the effect, problem, or death was not previously identified in nature, severity or degree of incidence in the

investigational plan, or application (including a supplementary plan or application) or any other unanticipated serious problem associated with peripheral nerve blockade that related to the rights, safety or welfare of subjects. Refer to the Peripheral Nerve Blockade Risk Analysis and Risk Assessment section for details on anticipated adverse regional blockade effects.

B. Adverse Event Reporting:

All serious adverse events will be reported to the IRB per IRB reporting requirements. These reports may include, but will not be limited to: date of onset; brief description of the events; their treatment; whether they resulted in death, inpatient hospitalization, severe or permanent disability or were life threatening; their relationship to the study device; and resolution. All unanticipated adverse device effects will be reported to the IRB.

C. Data Safety Monitoring Plan:

In an effort to ensure patient safety throughout the course of this study, a Data Safety Monitoring Plan has been established. The Data Safety Monitoring Committee shall convene at predetermined intervals to assess the progress of the study for potential patient-related adverse events. Such events include, but are not limited to: infection at the CPI catheter insertion site, infusion pump malfunction, local anesthetic toxicity, skin irritation or allergic reaction secondary to CPI catheter dressings, and falls secondary to motor blockade. Should 2 or more study-related adverse events occur, the study will be suspended immediately pending review of the study and results to date by the Data Safety Monitoring Committee. In addition, should any unforeseen study-related adverse event not previously reported in the literature occur, the study will be stopped for review by the Data Safety Monitoring Committee. Should the study be stopped at any point, enrollment will not resume until the Data Safety Monitoring Committee has determined that it is safe to resume the study. In addition, at any point during the course of the study should the Data Safety Monitoring Committee determine that it is not in the best interest of adolescent patients undergoing ACL with a hamstring autograft to continue the study, the study will be stopped.

D. Data Safety Monitoring Committee:

The Data Safety Monitoring Committee will meet to review the results of the study to date following the enrollment of the 30 participants, 60 participants, and 90 participants. In addition, the Data Safety Committee shall convene if 2 or more study-related adverse events occur related to this study. The Data Safety Monitoring Committee shall be comprised of 2 members of the Department of Anesthesia credentialed by CCHMC to perform peripheral nerve blockade but who are not part of this study ([name] and [name]), a statistician, and a patient advocate. The patient advocate will be the parent of a patient who has previously undergone ACL reconstruction at the Liberty Campus of CCHMC.

VIII. PRIVACY AND CONFIDENTIALITY

All subjects screened and enrolled in this study will be identified only by their initials and/or assigned study number only. Data confidentiality will be maintained by data being stored in a password protected computer and hard copies of subject information stored in a locked office. All information collected will be treated as confidential, as provided by law. The study records will be made available for review only to the Institutional Review Board (IRB) and the Food and Drug Administration (FDA). The subjects' names or any identifier will not be used in published information relating to this study.

IX. FUNDING

This is a CCHMC investigator initiated study that has received financial support from the AANA Foundation.

X. COST AND PAYMENT FOR PARTICIPATION

The patient's insurance company will be charged for all PNB and associated equipment utilized in this observational study. This is not a departure from standard practice of care, as PNB is routinely employed for postoperative pain control following ACL reconstruction with a hamstring autograft in the adolescent population.

Patients undergoing surgery with [name] will not receive any charges related to PNB as they will not receive PNB per his discretion.

The patient's insurance company may be charged for continuing medical care and/or hospitalization including tests and treatments of any side effects of the study treatment that may occur. In the event that the insurance does not cover all costs, patients may incur additional costs because of treatment side effects.

A \$20.00 gift card will be distributed as incentive to all participants who enroll in this study. The gift card will be mailed upon completion of the data collection process during the three days following surgery.

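### Section VI.B checks a parametric test of the 72-hour mean against Wilcoxon tests of 12-hourly scores, so the agreement check changes the outcome as well as the test, and V.D does not say which outcome its power refers to

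*Combined protocol and SAP*

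**What the plan says.** Section V.D (Sample Size Determination) reports that "The standardized effect size was calculated to equal 0.5". Taking alpha as 0.05 and power as 0.80, it concludes that "64 patients will be required for each treatment group based on anticipated difference in patient reported pain scores". This is raised to 70 per group for attrition. No mean difference, SD, time point or correlation between repeated scores is given.

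Section V.G (Data Collection) says "The patient or their guardian will record pain scores once every 6 hours for 72 hours postoperatively". Appendix B has 12 slots, from 6 to 72 hours.

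Section VI.B (Primary Endpoint Analysis) tests H1.a in two ways. The first averages each patient's scores and applies Pearson's correlation. For the second, "The Wilcoxon Mann Whitney test will also be used to analyze pain scores recorded at each 12-hour period". The stated reason for having both is the dispute over whether Likert-type data may be analysed parametrically. The section concludes: "Using both parametric and nonparametric tests will increase confidence when drawing conclusions should both tests lead to the same results". It does not say what counts as the same result when one test of the mean is set against six Wilcoxon tests.

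**The concern.** A comparison meant to show whether a finding depends on parametric assumptions should hold the outcome fixed and change only the test. Here both change. A mean of 12 imperfectly correlated scores has a smaller SD than a single score, so a given pain difference is generally not the same standardized effect on the two scales, and the power differs.

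For a true effect the test of the mean may be significant while several 12-hourly tests are not. A reader relying on the agreement statement could take that as a sign that the parametric result is fragile, when it says little about the Likert question. H1.a is the hypothesis on which the trial was sized, so the interpretation of its result should not rest on a check of this kind.

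**Working it through.** **Inputs from the documents.** Two-sided alpha 0.05 (VI.B), effect 0.5 and power 0.80 (V.D), 64 per group (V.D), 12 post-discharge scores (V.G, Appendix B), six 12-hourly times (VI.B).

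**Inputs assumed, because the documents give none.** Equal SD at each time, a common within-patient correlation ρ, and a time profile for the effect.

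**Step 1: the plan's own figure.** A two-sample t-test with d = 0.5, two-sided 0.05 and 80% power needs 63.8, so 64 per group. Power at 64 is 80.1%. Pearson's correlation between a two-level group variable and the mean score is equivalent to this t-test, so the sample size is right for a test of one outcome.

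**Step 2: 0.5 taken as the effect on the mean, effect constant over 72 hours.**

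SD(mean)/SD(single) = √((1 + 11ρ)/12), so single-time d = 0.5 × √((1 + 11ρ)/12).

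Wilcoxon power is taken as t-test power at 64 × 0.955 = 61.1 per group (efficiency for normal data).

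| ρ | SD ratio | single-time d | Wilcoxon power, one time |
|---|---|---|---|
| 0.3 | 0.599 | 0.30 | 38% |
| 0.5 | 0.736 | 0.37 | 52% |
| 0.7 | 0.851 | 0.43 | 65% |

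For ρ from 0.2 to 0.9 the range is 29% to 74%. If a 12-hour period means two 6-hourly scores pooled, it is 53% to 72% for ρ from 0.3 to 0.7. Simulation with scores rounded to 0-10 gave 34% to 64% per single-time test.

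**Step 3: same mean effect, but uneven over time.** If the effect covers 8 of the 12 scores, the difference at those times is 12/8 = 1.5 times the average difference. If it covers 4 of 12, it is 3 times.

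- Effect over the first 48 hours, or from 24 to 72 hours: power 69% (ρ = 0.3) to 94% (ρ = 0.7) where there is an effect, and 5% elsewhere.
- Effect from 24 to 48 hours only: nearly 100% at two times and 5% at the other four.

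**Step 4: 0.5 taken as a constant single-time effect.** Wilcoxon power at each time is 78%. The effect on the mean is 0.5 divided by the SD ratio. For ρ = 0.7 this is 0.5/0.851 = 0.587 (power 91%); for ρ = 0.3 it is 0.5/0.599 = 0.835 (power 99.7%).

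**Step 5: how often the analyses agree (simulation, 64 per group, 0.5 on the mean).**

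- Constant effect, ρ = 0.3 / 0.5 / 0.7: the mean and all six Wilcoxon tests are significant together in 3% / 16% / 34% of trials. Among trials where the mean is significant, that is 0.028/0.802 = 3%, 0.158/0.814 = 19% and 0.335/0.788 = 43%.
- Uneven effects as in Step 3: the mean and all six together in about 1% of trials or fewer.
- The mean and at least one of six, constant effect: 75% to 80%, close to the power of the mean test alone. Six tests at 0.05 have a chance of at least one false positive bounded only by 6 × 0.05 = 0.30.
- One Wilcoxon test on the same per-patient mean: about 75% to 80% power, and the same significance result as the parametric test in about 95% of trials.

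**The case against.** The strongest case against is that nothing in V.D is miscalculated and that the plan never promises 80% for each 12-hourly test. That stands.

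Three stronger readings might be inferred, and the documents support none of them.

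- **That 80% power cannot hold for both analyses.** If 0.5 is a constant single-time effect, the Wilcoxon tests have about 78% and the test of the mean has 91% or more. Nor is it impossible for 0.5 to describe both outcomes. With an effect over 8 of 12 scores and ρ = 0.4, single-time d at the affected times is 0.5 × 1.5 × √(5.4/12) = 0.50.
- **That every 12-hourly test has only about 40% to 65% power.** This needs a constant effect, which the plan's rationale does not suggest. Section I says single injection can last up to 24 hours and that only the continuous block reliably covers later days. Section V.A has the catheter in place for 48 hours.
- **That disagreement would formally weaken the conclusion.** VI.B says only that agreement adds confidence. It sets no decision rule. How often agreement fails depends on a threshold that the plan does not contain.

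It is also fair to say that the 12-hourly comparisons bear on duration of analgesia, which is the research question, so they should not be dropped.

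None of this rescues the agreement check. Under constant and uneven effects alike, it compares different outcomes while being justified as a comparison of test types.

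**Conclusion.** The point holds as a fault of specification and method, not as an arithmetic error. The agreement check in VI.B cannot answer the question it is there to answer, because the outcome changes along with the test. V.D leaves open which outcome its 0.5 and 0.80 describe.

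The size depends on assumptions outside the documents. With 0.5 on the 12-score mean, equal SDs, a constant effect and ρ of 0.3 to 0.7, single-time Wilcoxon power is about 38% to 65%. With an uneven effect it runs from about 5% to nearly 100%. A rule requiring all six tests to agree would usually fail for a true effect. A one-of-six rule would add almost no hurdle to the test of the mean and would bring in uncorrected multiplicity. The conclusion that the check does not isolate parametric assumptions needs none of these figures.

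**What to change.** - **VI.B, agreement check:** run the nonparametric check of H1.a as one Wilcoxon test on the same per-patient 72-hour mean used for the parametric test, and base the agreement statement on that pair only.
- **VI.B, time course:** keep the 12-hourly Wilcoxon comparisons as secondary analyses of how the difference develops over time, outside the agreement check. State whether a 12-hour period is a single score or two 6-hourly scores pooled.
- **V.D:** say which pain outcome the 0.5 and the 80% power refer to, with the mean difference and SD behind the 0.5 and, if it is the mean, the correlation assumed. The 38% to 65% range should not be written into the protocol as a fixed figure, because it rests on assumptions made here for illustration.

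The cost is a wording change and one extra test on data already being collected. The sample size does not change on this account.
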